8.3 Stratification

Before randomization, subjects will be stratified by site, age (< 18 years or ≥ 18 years) and by severity of ACS (defined below). Stratification by age and severity of ACS will be done to ensure balance across treatment groups. Strata will not be adequately sized (i.e., powered) to analyze the primary endpoint in each stratum.

Mild to moderately severe ACS is defined by all the diagnostic criteria for ACS listed in the subject eligibility section in addition to the following:

- transcutaneous oxygen saturation of ≥ 85% in room air, and
- segmental or lobar infiltrates that involve no more than two lobes by chest radiography.

Severe ACS is defined by all the diagnostic criteria for ACS listed in the subject eligibility section and one or more of the following:

- impending respiratory failure or need for invasive or non-invasive ventilatory support,

- transcutaneous oxygen saturation of $< 85\%$ in room air or $\leq 90\%$ despite maximal supplemental oxygen, or
- segmental or lobar infiltrates that involve three or more lobes by chest radiography.

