9.2 Randomization and Masking

After enrollment, subjects will be randomized to one of two treatment arms. Subjects in Arm 1 will receive oral dexamethasone. Subjects in Arm 2 will receive oral placebo. A computer-generated, adaptive randomization schema will be used to allocate subjects 1:1 between the two treatment arms. Randomization will be stratified by site, age and the severity of ACS (see Section 8.3). In order to increase the likelihood of balance in treatment allocations, subjects will be randomized using the standardized range variation (79) of the sequential allocation algorithm of Pocock and Simon (80), a minimization method. This method attempts to achieve treatment balance on several subject characteristics (i.e. age group, site, and severity of ACS in this study) simultaneously – not within separate strata. Minimization consists of biasing the treatment allocation so as to minimize the total imbalance between the treatment groups on some scale (81). The order of entry of the subjects to the various centers and in the various prognostic groups is assumed to be random. As minimization is a dynamic method that uses information on subjects already entered to allocate treatment to the next subject, a continuous updating of the information related to previous treatment allocations is required, thus a centralized randomization system will be used.

Pharmacists at each center will be unblinded and will utilize information from the interactive voice/web randomization system (IVRS) at the SDMC to obtain a new treatment assignment for a subject and provide each subject with appropriate dosing of both therapies. The IVRS system has the capability of providing unblinding information in case of a medical emergency where the exact study drug is needed in order to appropriately treat a subject.

The time interval between Randomization and the first dose of study drug administration will be no longer than 2 hours. In the event a subject's first dose occurs outside the 2-hour time limit, the subject will still be included in the study and the analysis. This is in the spirit of the intention-to-treat analysis. The amount of time in excess of the 2-hour limit until the first dose of study drug will also be recorded. This event will be documented as a protocol deviation.

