13.2.2 Efficacy Analyses

All efficacy analyses will be performed on the ITT population while the primary and some secondary analyses will be repeated on the per-protocol population. Center will be included in the models as permitted by sample size. Center will be eliminated from the models if it appears to be an insignificant variable in the model.

The primary analysis will compare the duration of ACS signs and symptoms (as assessed by the ACS assessment, Appendix3) or the duration of hospitalization for ACS, whichever happens first, of subjects in the dexamethasone treated arm to those in the placebo treated arm. The symptom/hospitalization duration for subjects with ACS will be summarized by treatment group, severity strata, and age strata. The effect of treatment on symptom/hospitalization duration will be tested using a Generalized Linear Mixed Model (GLMM) with the natural log of symptom/hospitalization duration as the outcome variable. The SAS[®] procedure MIXED will be used to fit the GLMM. The GLMM will include treatment, age group, and severity as fixed effects. The GLMM will not specify any variables as random effects or repeated effects, but it will use the GROUP option in the REPEATED statement to estimate separate error variances for each treatment (i.e., GROUP = “treatment”). The SAS[®] procedure MIXED will be used to fit the GLMM.

The GLMM model specified above is necessary for the primary analysis because pilot data give evidence that the length of stay (LOS) in the hospital (which is assumed to be similar to duration of symptoms) for ACS has a lognormal distribution. If the LOS for ACS is distributed as lognormal in each treatment group, then the model of the natural log of LOS must allow for differences in treatment group variances as well as for treatment group mean differences. By allowing for differences in treatment group variances and treatment group means, the treatment group specific distributions can be correctly estimated under the lognormal assumption, resulting in a correct comparison of treatment group means.

As a secondary analysis, parametric survival analysis techniques will be used to estimate distributional parameters and model the hazard function of symptom duration/LOS/hypoxemia/fever for each treatment group. The time to the event of interest (e.g., symptom duration) will be described using a Kaplan-Meier plot stratified by treatment.

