The effects of dexamethasone on secondary clinical endpoints of duration of hospitalization, supplemental oxygen therapy (or hypoxemia), and fever will be summarized by treatment group, severity strata, and age strata and evaluated by using a similar GLMM as the primary analysis. The secondary clinical endpoints of the amount of opioid usage, the number/type of transfusions, pulmonary function and pulmonary radiograph findings, the number of rebound hospitalizations, and pain scores, will be summarized by treatment group, severity strata, and age strata. The effects of dexamethasone treatment on these outcome variables will be evaluated using:

- GLMM with treatment, age group, severity, and timepoint as fixed effects and subject as a random effect for the longitudinal pain scores;
- Wilcoxon Rank test for rebound hospitalizations and number of transfusions;
- T-Test (or Wilcoxon Rank test if assumptions are not met) for the amount of opioid usage and all pulmonary function outcomes;
- Cochran-Mantel-Haenszel Chi-square test for radiographic findings (resolved, improved, unchanged, worse).

The secondary endpoints of the laboratory variables (VCAM₁, ICAM₁, P-selectin, L-selectin, vWF multimers, endothelial and monocyte microparticles, WBTF, NO, and sPLA₂) will be summarized by measurement timepoint, treatment group, severity strata, and age strata. The overall change from baseline for each of the collected measurements over time will be modeled using a random effects longitudinal mixed model, with treatment, baseline measurement, age group, and severity as fixed effects and subject as a random effect. This class of model allows us to control for the correlation induced by having multiple measurements on an individual. Estimates of the treatment difference over time will be depicted by displaying the estimated means of each treatment group over time. Descriptive p-values for comparisons of interest will also be produced.

All meaningful subject data collected in the CRFs will be provided in data listings. All statistical analyses will be performed using the SAS[®] System.

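### Opioid amount, pulmonary function and transfusions are tested without the age and severity factors used in allocation: a minor loss of precision that costs almost nothing to avoid

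*Protocol*

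**What the plan says.** Protocol Section 9.2 allocates by minimization: "Randomization will be stratified by site, age and the severity of ACS". Section 8.3 gives the same factors.

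Section 13.2.2 uses age group and severity for most endpoints:

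- Primary endpoint: "The GLMM will include treatment, age group, and severity as fixed effects". The secondary durations get a similar model.
- Pain: "GLMM with treatment, age group, severity, and timepoint as fixed effects and subject as a random effect for the longitudinal pain scores".
- Biomarkers: a longitudinal mixed model that contains both factors.

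The remaining numeric endpoints get two-group tests with no covariate or stratum:

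- "T-Test (or Wilcoxon Rank test if assumptions are not met) for the amount of opioid usage and all pulmonary function outcomes"
- "Wilcoxon Rank test for rebound hospitalizations and number of transfusions"

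For these endpoints, age and severity appear only in the descriptive summaries. Section 13.3.1 names the two factors as covariates for the primary analysis and adds that others may be considered for clinical outcomes. Section 13.3.3 makes every p-value other than the primary one descriptive.

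**The concern.** Minimization forces the arms to be alike on age group and severity, which removes part of the chance variation in the treatment difference. A two-group test does not know this. It leaves variation between age and severity groups in its error term, so the reported standard error is larger than the true one. Intervals are then too wide and the test rejects less often than its nominal level. This is one mechanism, not two separate losses.

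The endpoints concerned are ones where the factors plausibly matter. Entry runs from age 5 into adulthood (Section 8.1). Lung function is listed as FVC, FEV1, FEF25-75% and PEFR without saying whether in absolute units or percent predicted. Opioid use is listed as an amount with no stated scaling to weight. The exchange-transfusion indications in Section 9.1.5 overlap the definition of severe ACS in Section 8.3. At stake is the precision of secondary results that bear on the morbidity and pulmonary function objectives.

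**Working it through.** **1. The plan's own figure.** No power or sample size is stated for these endpoints. The only sizing figure is the primary one in Section 13.4: 54 per arm, 56 with withdrawals. With log-scale SDs of 0.6 and 0.3, a difference of 4.25 − 3.95 = 0.30, two-sided alpha 0.05 and 90% power, the normal approximation gives (0.36 + 0.09)(1.960 + 1.282)² / 0.09 = 52.5, so 53. The Satterthwaite t-test gives 89.5% power at 53 and 90.07% at 54. The figure reproduces, and 56 per arm is used below.

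**2. Variance explained by age group.** Let p be the adult share and D the adult-child gap in within-group SDs. Then

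R² = p(1−p)D² / (1 + p(1−p)D²), and the ratio of adjusted to unadjusted standard error is √(1−R²).

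Section 7.1.2 allows up to 112 children and anticipates at most 56 adults, so 56/168 = 1/3 is a ceiling for p if the pediatric target is filled. Lower shares are assumptions, and so is D: the protocol gives no such gap.

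| p | D | p(1−p)D² | R² | SE ratio | SE reduction |
|---|---|---|---|---|---|
| 0.10 | 1 | 0.090 | 0.083 | 0.958 | 4% |
| 0.20 | 1 | 0.160 | 0.138 | 0.928 | 7% |
| 1/3 | 1 | 0.222 | 0.182 | 0.905 | 10% |
| 1/3 | 2 | 0.889 | 0.471 | 0.728 | 27% |

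**3. Effect on nominal power.** At 56 per arm an unadjusted test has 80% power for (1.960 + 0.842)√(2/56) = 0.529 SD. Adjusted power is Φ(2.802/√(1−R²) − 1.960): 84.0% at R² = 0.10 and 87.9% at R² = 0.20.

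**4. Effect under minimization.** There were 3,000 simulated trials of 112 subjects per setting. The assumptions were biased-coin minimization with probability 0.8, 10 sites, one-third adults and one-quarter severe. R² here is for age group and severity together, split equally. The effect was sized for a nominal 80% adjusted power.

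| R² | Size, t-test | Size, adjusted | Power, t-test | Power, adjusted |
|---|---|---|---|---|
| 0 | 4.7% | 4.6% | 81% | 80% |
| 0.10 | 3.7% | 4.6% | 76% | 80% |
| 0.20 | 2.3% | 3.8% | 71% | 78% |
| 0.30 | 2.3% | 4.8% | 66% | 79% |

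The Monte Carlo error on a 5% rate is √(0.05 × 0.95/3000), about 0.4 points. The t-test becomes conservative as the factors become prognostic; the adjusted model stays near nominal. The Wilcoxon test was not simulated; the same direction is expected by the same mechanism.

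**5. Rebound.** With a factor held by one-third of subjects, an odds ratio of 2 to 5 and an event rate of 5 to 15% (all assumed), R² is only about 0.6 to 8%. Appendix 2 expects 8, 6 and 4 rebounds in total in scenarios C, D and E. Spread over four age-by-severity cells, that leaves little to stratify.

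**The case against.** The other side has a fair case:

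- **The tests are valid.** They err on the conservative side, no power is claimed for these endpoints, and Section 13.3.3 makes their p-values descriptive. This stands and fixes the weight of the point.
- **The protocol leaves room.** Section 13 refers detail to the SAP, and Section 13.3.1 permits other covariates. This softens the point, but an optional sentence that names no endpoint does not replace tests that Section 13.2.2 names outright.
- **The gain may be small.** Percent-predicted lung function would already remove much of the age effect, as would opioid amounts per kg. Neither scale is stated, so this stands as a limit on size.
- **Rebound is already treated as yes/no.** Section 11.6.6 does so for quarterly monitoring, and on nearly binary data a Wilcoxon test is close to comparing two proportions. This stands: the case for changing the rebound analysis is a readable effect estimate, not precision.

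A reader might infer a loss equivalent to 22 to 89% more subjects. That is 1/(1−R²) at R² of 0.18 and 0.47, which needs the adult share at its ceiling and a gap of 1 to 2 SD. The documents support neither as a planning value, and the range cannot be carried over to rebound or transfusions.

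**Conclusion.** The point holds as a minor efficiency and consistency improvement for opioid amount, pulmonary function and number of transfusions. The same section adjusts its other endpoints for factors that drive allocation and gives no reason for omitting them here.

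The direction is firm wherever age group or severity is prognostic; the size is an assumption. With a 1 SD gap and 10 to 33% adults, the standard error would be about 4 to 10% smaller after adjusting for age group. At combined R² of 0.10 to 0.20 under minimization, the t-test's true size was 3.7 to 2.3% against 5%, with 4 to 7 points less power than the adjusted model. No separate estimate is available for transfusions.

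A reader might also infer that false positives are inflated or that the trial's conclusion is threatened. Neither follows: the unadjusted tests are conservative, and the primary analysis already contains both factors.

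**What to change.** In Section 13.2.2, or in the SAP with a pointer from it, before unblinding:

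- **Pulmonary function and opioid amount:** linear models with treatment, age group and severity, on the log or rank scale if skewed, with the treatment estimate and confidence interval. If lung function is analysed in absolute units, continuous age may replace age group.
- **Number of transfusions:** a Wilcoxon (van Elteren) test stratified by age group and severity.
- **Rebound:** final comparison of any rebound, yes/no per subject as in Section 11.6.6, with a risk difference and confidence interval.

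The models should not depend on height, because it is not among the evaluations listed in Section 10.3 and Table 10.2. Age group and severity are already recorded for allocation, so the cost is wording and programming, with no new data, visits or subjects.

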13.2.3 Safety Analyses

Safety analyses will be performed on all randomized and dosed subjects (i.e., the ITT population). An analysis of safety will include a summary of AEs, SAEs, vital signs, clinical laboratory tests (CBC and reticulocyte count), physical examination, urine output and daily fluid balance, blood culture, peripheral oxygen saturation, and baseline and interim history. All safety outcomes will be summarized by treatment, age strata, and measurement time point (if appropriate).

Treatment-emergent AEs, drug-related AEs, SAEs, and drug-related SAEs (as determined by the investigator) will be classified using the Medical Dictionary for Regulatory Activities (MedDRA, Version 6.0 or later) preferred terms. A treatment-emergent AE is one that started or worsened in severity after initial administration of study drug. All treatment-emergent AEs and SAEs will be classified with regard to severity and duration of the event. These data will be summarized by treatment group, age strata, body system, and preferred terms within a body system. AE comparisons across treatment groups, stratifying on age group, will be made using a Chi-square test on any AEs that occur in more than 10% of the subjects. Each occurrence of an AE (classified on the basis of MedDRA terminology) will be reported separately for a given subject.

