10.3.2 Evaluations During Study

The elements of the ACS assessment will be assessed and recorded every 4 hours (Appendix 3). Note: Time Zero is defined as the initial dose of study drug and the first 24 hour period begins with the first dose. All subsequent doses and study assessments

are scheduled from this time point. The first every 4 hour ACS assessment begins as close as possible to 4 hours after the first dose of study drug and the next routine nursing assessment. The studies required on a daily basis include a CBC and a reticulocyte count. Follow-up blood cultures are obtained at the discretion of the attending physician but should be considered every 24 hours if the subject is persistently febrile (temperature $\geq 38.5^{\circ}\text{C}$). A daily weight, physical exam, and vital signs (every 4 hours which includes blood pressure) will be recorded on the subject's medical record. Subjects will be monitored by continuous pulse oximetry until there has been no requirement for supplemental oxygen for 24 hours and there is clinical improvement. Oxygen saturation (O_2) will be recorded at least every 4 hours with the vital signs until pulse oximetry is stopped. A semi-quantitative, age-appropriate rating of pain intensity [the 0-10 Oucher Scale (age < 10 years) or the 0-10 numeric rating scale (age ≥ 10 years)] will also be obtained by the nurse and recorded with each set of vital signs. A follow-up chest radiograph is not required, but it can be obtained if clinically appropriate. The daily amount and type of opioid analgesia as well as the number and types of transfusions will be recorded. Accurate, cumulative fluid balance measurements (ins and outs) will be recorded every 8 hours on the subject's medical record. AEs will be recorded as they occur throughout hospitalization. The duration of fever, hypoxemia, and hospitalization will also be recorded. Table 10.2 summarizes these evaluations. Furthermore, blood samples will be drawn for the central laboratory measurements at Baseline and Days 1, 2, and 8 (See Table 10.1.).

Table 10.2 Clinical and Clinical Laboratory Evaluations and Procedures

	Inpatient				Inpatient or Outpatient	
	Baseline	Daily	Inter- mittent	Contin- uous	Follow-up #1(7- 10 d) ⁶	Follow-up #2 ⁶
ACS assessment ¹	X		Every 4h		X	X
History	X				Interval ²	Interval ²
Physical exam	X	X				X
Weight	X	X				X
Vital signs	X		Every 4h ⁵		X	X
CBC, reticulocyte count	X	X			X	X
Blood culture	X	X ³				
Chest radiograph	X					X

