11.2 Adverse Events

An adverse event (AE) is defined for this study as any untoward medical occurrence in a subject or clinical investigation subject administered a pharmaceutical product that does not necessarily have a causal relationship with this treatment. An AE can therefore be any unfavorable and unintended sign (including an abnormal laboratory finding), symptom, or disease temporally associated with the use of a medicinal (investigational) product, whether or not related to the medicinal (investigational) product. AE data are recorded on the CRF.

Examples of an AE include:

- Exacerbation of a chronic or intermittent pre-existing condition including either an increase in frequency or intensity of the condition.
- Significant or unexpected worsening or exacerbation of the condition/indication under study.
- A new condition detected or diagnosed after study drug administration even though it may have been present prior to the start of the study.
- Signs, symptoms, or clinical sequelae of a suspected overdose of either study drug or a concurrent medication (“overdose” per se, should not be reported as an AE/SAE).
- Pre- or post-treatment events that occur as a result of protocol-mandated procedures (e.g., invasive protocol-defined procedures, modification of a subject’s previous drug treatment regimen).

An AE does **not** include

- Medical or surgical procedures (e.g., colonoscopy, biopsy). The medical condition that leads to the procedure is an AE.
- Social or convenience hospital admissions where an untoward medical occurrence did not occur.
- Day to day fluctuations of pre-existing disease or conditions present or detected at the start of the study that do not worsen.
- The disease/disorder being studied, or expected progression, signs, or symptoms of the disease/disorder being studied unless more severe than expected for the subject’s condition.

11.2.1 Adverse Events related to Increased Blood Pressure.

All site Principal Investigators are required to review blood pressure results at study enrollment, once daily during hospitalization, and at both follow-up clinic visits. The following blood pressure results must be reported as Adverse Events:

- A single blood pressure in which the systolic pressure is ≥ 140 mmHg ***and*** the diastolic pressure is ≥ 90 mmHg;
- a systolic pressure ≥ 140 mmHg on 2 more occasions in a rolling 24 hour period regardless of diastolic pressure;

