11.6.4 Reporting of All Adverse Events (Serious and Non-serious)

Six months after the first subject is enrolled in the study, and at the end of each 6 month period thereafter, the SDMC will:

- Use the current version of the MedDRA dictionary to code all AEs that have been recorded on study AE forms.
- Make a “snapshot” copy of the AE data, including MedDRA codes.

- Create frequency tables of treatment x occurrence (yes or no, since inception of the study) of all subjects. One table will be created for each highest-level MedDRA term for which AEs have been reported. The counting units are subjects, not events.
- Compute Fisher's Exact Test (FET) statistic to test the alternative hypothesis that occurrence of AEs is not independent of treatment group. The FET p-value is not adjusted for multiplicity.
- If the FET p-value is less than the critical value shown in Table 11.3 and the active treatment group has a higher AE rate, the SDMC will conduct further statistical analyses as indicated by the circumstances and alert the DSMB to this finding in the semi-annual DSMB report.
- Collaborate with the PI to incorporate the results into the study's semi-annual report to the DSMB and the NHLBI Project Officer.

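### Blood-pressure adverse events are detected mainly in hospital but compared as ever/never proportions, so a shorter dexamethasone stay could understate them by anything from nothing to about a third

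*Protocol*

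**What the plan says.** **Measurement.** In hospital, section 10.3.2 has "vital signs (every 4 hours which includes blood pressure) will be recorded on the subject's medical record". After discharge, Table 10.2 and section 10.3.3 schedule blood pressure at two clinic visits: one on days 7-10, after study drug is complete, and one about 30 days after discharge. Section 9.1.6 has the remaining doses taken at home.

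**AE rules.** Section 11.2.1 has investigators review blood pressure at "study enrollment, once daily during hospitalization, and at both follow-up clinic visits". One rule is met by a single reading with both systolic and diastolic pressure raised. The other two need a raised systolic, or a raised diastolic, on repeat occasions within a rolling 24 hours.

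**Comparison.** Section 13.2.3 states: "AE comparisons across treatment groups, stratifying on age group, will be made using a Chi-square test on any AEs" seen in more than 10% of subjects. The start of the window is fixed: "A treatment-emergent AE is one that started or worsened in severity after initial administration of study drug". No common end is given. In the periodic monitoring tables of sections 11.6.3 and 11.6.4, subjects are classed yes or no since the study began: "The counting units are subjects, not events".

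**Expected stay.** Section 13.4 plans for a stay 30 hours shorter on dexamethasone.

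**The concern.** A subject-level proportion is a fair comparison when both arms are watched for events equally long and equally closely. Here the close watching stops at discharge, and earlier recovery, which normally brings earlier discharge, is the benefit under test. If dexamethasone works, its arm has fewer inpatient readings, and no blood pressure is scheduled at home while the taper continues. The two repeat-reading rules can hardly be met at a single clinic visit.

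Raised blood pressure is a known steroid effect, and new hypertension needing treatment is a discontinuation criterion in sections 8.4 and 11.7. A comparison that leans towards fewer such events on active drug weakens what the trial can say about steroid hypertension.

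**Working it through.** **1. The plan's own figure.** Section 13.4 assumes log-scale means of 4.25 (placebo) and 3.95 (dexamethasone), SDs of 0.6 and 0.3, two-sided alpha 0.05 and 90% power. With 54 per arm:
- SE = √((0.36 + 0.09)/54) = 0.0913, and noncentrality = 0.30/0.0913 = 3.29.
- Satterthwaite df = 53 × 0.45²/(0.36² + 0.09²) = 77.9.
- Power is 90.07%; with 53 per arm it is 89.5%. The stated 54 is reproduced.

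**2. Expected inpatient time.** The lognormal mean is exp(μ + σ²/2).
- Placebo: exp(4.25 + 0.18) = 83.9 h. Dexamethasone: exp(3.95 + 0.045) = 54.3 h.
- The difference is 29.6 h (stated as 30) and the ratio is 0.65, so mean time is 35% shorter.
- Medians are 70.1 and 51.9 h, 26% shorter.
- From Table 13.1, the two earlier trials give 1 − 47/80 = 41% and 1 − 60/87 = 31%.

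**3. Scheduled readings.** One per 4 h plus two visits: 83.9/4 + 2 = 23.0 against 54.3/4 + 2 = 15.6, which is 32% fewer.

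**4. Effect on the proportion.** The protocol gives no AE rates, so the placebo proportion and the true hourly rate ratio (HR) are assumptions. Take stay T from first dose, a constant hourly rate λ and no detection after discharge:
- P(event) = E[1 − exp(−λT)], with λ set to give the assumed placebo proportion.
- Shown on dexamethasone: E[1 − exp(−HR·λ·T)] over dexamethasone stays. With equal observation: the same over placebo stays.
- Understatement = 1 − shown/equal.

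| Placebo | HR | Dexamethasone shown | Risk ratio shown | Risk ratio, equal observation | Understatement |
|---|---|---|---|---|---|
| 5% | 1 | 3.3% | 0.66 | 1.00 | 33.9% |
| 10% | 1 | 6.7% | 0.67 | 1.00 | 32.7% |
| 10% | 2 | 13.0% | 1.30 | 1.87 | 30.4% |
| 20% | 1 | 14.0% | 0.70 | 1.00 | 30.1% |
| 20% | 1.5 | 20.2% | 1.01 | 1.40 | 27.9% |
| 20% | 2 | 25.9% | 1.29 | 1.74 | 25.8% |
| 50% | 2 | 62.7% | 1.25 | 1.43 | 12.4% |
| 50% | 3 | 76.5% | 1.53 | 1.65 | 7.3% |

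**5. Relaxing the assumptions.**
- Steroid effect only in the first 48 h, HR 2: 20% (10% placebo) and 18% (20% placebo).
- Hourly rate that falls with time: 24% at a 96 h half-life, 16% at 48 h, 7% at 24 h and 1% at 12 h.
- Share of post-discharge events still found, in an 8-day window: 26% understatement if 10% are found, 18% if 25%, 10% if 50%, and 0% if all.

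**6. A common 48 h window.** Mean monitored time is E[min(T, 48)] = exp(μ + σ²/2)·Φ((ln 48 − μ − σ²)/σ) + 48·(1 − Φ((ln 48 − μ)/σ)).
- Planning values: 44.5 h placebo, 44.6 h dexamethasone.
- With the Table 13.2 values of the earlier trials: 44.4 and 41.2 h (7% shorter), and 43.1 and 41.4 h (4% shorter).
- The window therefore removes most or all of the difference.

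**The case against.** **Detection after discharge is not nil.** The single-reading rule can be met in clinic, and section 10.3.3 captures AEs after discharge. This stands, and it is why a third is a ceiling. It does not restore readings during the home taper, because none is scheduled.

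**Readmission works the other way.** The earlier trials had 6 against 1 and 10 against 2 readmissions, more on dexamethasone. Readmission adds inpatient observation in that arm. This stands; the calculation counts only the index stay, and the taper is meant to reduce readmissions, so the offset cannot be sized.

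**Dosing is front-loaded.** The high-dose phase ends at 2 days or at discharge, so it is observed in hospital. This lowers the figure, as step 5 shows.

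**Some illustrations fall below the 10% threshold.** If the threshold applies to both arms pooled, 10% and 6.7% average about 8.4% and no test is run. The 20% rows are the better guide to the quoted test.

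**Section 13.2.3 summarizes safety outcomes by time point, and details belong in the SAP.** The time-point summary is descriptive and does not alter the test. The SAP is not at hand and may add windows, but the protocol itself names the test and its subject-level basis.

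**Leukocytes.** A reader might infer that leukocytosis is hidden in the same way. The documents do not support that. No count is defined as an AE; the 50,000/mm³ figure in section 9.1.2 only triggers a change in the study-drug schedule. Laboratory values have their own comparison (section 11.6.5; Table 11.4 specifies change from baseline), and both arms have a CBC at both visits.

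**Conclusion.** The concern holds for blood-pressure AEs. The measurement schedule, two of the three AE rules, the ever/never comparison and the planned shorter stay together lean towards understating these events on dexamethasone.

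If the stay shortens as planned, the understatement is at most about a third. That needs uncommon events, a constant hourly rate and no detection after discharge. It is roughly 7% to 30% under other plausible assumptions, smaller still if the rate falls very quickly, and zero if post-discharge detection is complete. If the stay does not shorten, the problem does not arise.

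Two stronger readings are not supported:
- **That a third of steroid toxicity is hidden.** The 35% is a difference in inpatient time, and no AE rates are given that would turn it into a known bias.
- **That the DSMB alert is biased by a known amount.** Sections 11.6.3 and 11.6.4 tabulate by highest-level MedDRA term, which can mix blood-pressure events with others, so the effect on the alert has not been quantified.

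**What to change.** In section 13.2.3 and the DSMB report:
- Add a comparison of subjects with a blood-pressure AE over a common window, first dose to 48 h.
- Report inpatient and follow-up blood-pressure AEs separately by arm.
- Give rates per inpatient day as description only. They condition on length of stay, which is determined after randomization, and longer-staying subjects weigh more.
- Keep the planned subject proportions.

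No clinical procedure changes. First-dose time is already Time Zero and discharge time is already needed for the primary endpoint. The one point to confirm is that the AE form records onset closely enough to place an event inside or outside 48 h.

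The cost is some programming. The 48 h window has fewer events and does not cover the taper. Under the planning values about 26% of placebo and 40% of dexamethasone subjects leave before 48 h, so the arms match in mean monitored time, not subject by subject.
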